5.2 Secondary Objectives

Secondary objectives are to:

1. Compare outcome on XR-NTX versus BUP-NX for the following domains:
 - a. Proportion successfully inducted onto assigned medication.
 - b. Safety, as measured by adverse events and serious adverse events, including opioid overdose episodes, both during the 6-month trial and during the 3-month follow-up period.
 - c. Opioid abstinence, as measured by the Timeline Follow-Back (TLFB) (self-report days using opioids), proportion of opioid-positive urine tests.
 - d. Misuse of alcohol and other drugs of abuse (e.g., cocaine, other stimulants, cannabis, benzodiazepines), by self-report and urine drug screens.
 - e. Tobacco use, as measured by the Fagerström Test for Nicotine Dependence (FTND).
 - f. Craving for opioids, and for other drugs, measured by Visual Analog Scales (VAS).
 - g. Depressive, anxiety, and subacute withdrawal symptoms (typical constellation is fatigue, anorexia, and insomnia), as measured by the Hamilton Depression Scale (17-item) (HAM-D) and the Subjective Opioid Withdrawal Scale (SOWS).
 - h. Problems related to drug abuse, as measured by the Addiction Severity-Index-Lite (ASI-Lite) and EuroQol (EQ-5D).
 - i. HIV risk behavior over time, as measured by the Risk Assessment Battery (RAB).
 - j. Cognitive function, as measured by performance on brief pen and paper tasks (Trail Making Test Parts A and B, Stroop).
2. Explore baseline demographic, clinical, and genetic features as predictors of opioid use outcome over the 6-month trial (main effect of predictors), and as moderators of differential treatment effect (moderator by treatment interaction).
3. Collect a limited dataset to permit analyses of economic costs and benefits of the two treatments.

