3.6 Analysis Populations

Each primary and secondary efficacy outcome measure will be analyzed for the intent-to-treat (ITT) and evaluable population. The intent-to-treat principle is that participants will be analyzed in the groups to which they were randomized, regardless of whether they received the randomized study medication. Another analysis population of interest is the as-treated population. The as-treated population will consist of only participants who were inducted onto study medication.

Major differences in the results for the ITT and as-treated populations, if any, will be further explored. While there is every intention to be complete in describing the analyses to be performed, it is not possible to anticipate every contingency, and some adjustments may be required to meet constraints posed by the structure of the data. Constraints such as non-linearity, non-normality, etc. may lead to different but more appropriate approaches to analysis.

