5.5 Secondary Outcomes

Most secondary outcome analyses will follow a similar form and strategy to that above, with different linear models as appropriate for the form of the secondary outcome variable: dichotomous secondary outcomes will use logistic regression; time-to-event variables will use survival analysis with Cox models; continuous variables or count variables (e.g., bags per day of heroin use) will use mixed effect models depending on the distribution of the outcome (e.g., normal, Poisson, negative binomial, zero-inflated). Repeated measures will have time in the model in addition to treatment and baseline covariates.

For the secondary outcome measures that are continuous a mixed effects model will be used to analyze the data incorporating appropriate covariates. The model for secondary outcomes that are continuous can be explained in matrix form as follows:

$$\begin{aligned} \mathbf{y} &= \mathbf{X}\boldsymbol{\beta} + \mathbf{Z}\mathbf{b} + \boldsymbol{\varepsilon} \\ \mathbf{b} &\sim N_q(0, \boldsymbol{\Psi}) \\ \boldsymbol{\varepsilon} &\sim N(0, \sigma^2 I) \end{aligned}$$

Where

- \mathbf{y} is the N (sample size) \times 1 secondary outcome vector.
- \mathbf{X} is the $N \times p$ model matrix for the fixed effects (e.g. Treatment).
- $\boldsymbol{\beta}$ is the $p \times 1$ vector of fixed-effect coefficients.
- \mathbf{Z} is the $N \times q$ model matrix for the random effects (e.g. Site).
- \mathbf{b} is the $q \times 1$ vector of random-effect coefficients.
- $\boldsymbol{\varepsilon}$ is the $N \times 1$ vector of errors for outcome.
- $\boldsymbol{\psi}$ is the $q \times q$ covariance matrix for the random effects.
- $\boldsymbol{\sigma}^2$ is the $N \times N$ covariance matrix for the errors.

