¹ A participant is defined as not having relapsed if by the Week 24 visit, the participant did not meet any of the relapse criteria.

² Time to relapse summary statistics are only summarized for subjects who met the relapse criteria.

[figure not shown]
³ Participants do not provide TLFB data while in detox.

Figure 5A: TLFB and UDS for Day 0 to Day 21
Figure 5A: UDS for Day 0 to Day 21- Treatment=BUP-NX

Figure 5B: UDS for Day 0 to Day 21- Treatment=XR-NTX

[figure not shown]
Figure 5C: TLFB for Day 0 to Day 21- Treatment=BUP-NX

Figure 5D: TLFB for Day 0 to Day 21- Treatment=XR-NTX

Separate figures will be generated for TLFB and UDS and additionally separate for each treatment arm. Each row in the figure would correspond with a participants TLFB and UDS results only from Day 0 to Day 21. The legend would indicate that the green vertical dashes indicate no illicit opioid use on TLFB whereas the yellow vertical dashes indicate illicit opioid use. The red +, - and o values indicate UDS results of positive for non-protocol defined opioids, negative for non-protocol defined opioids and missing UDS results respectively. The figure colors will be modified to accommodate color blind readers.

Figure 6: Kaplan-Meier Plots of Time to Relapse by Treatment Arm
Example Kaplan-Meier figure provided below.

The x-axis for the Time to Relapse Kaplan-Meier Plots will be measured in days. Separate curves on the same plot will be defined as the treatment arms. Censored observations will be represented using a + sign.

Table 16: Summary of Primary Outcome (Time to Relapse¹) for Groups of Interest						
	BUP-NX (N=)			XR-NTX (N=)		
	N	Mean (STD)	Median (Min, Max)	N	Mean (STD)	Median (Min, Max)
Randomization Timing Status						
Early Randomizers						
Late Randomizers						
Opioid Severity Level						
Low Severity						
High Severity						
Randomization Timing Status by Opioid Severity Level						
Early Randomizers and Low Severity						
Early Randomizers and High Severity						
Late Randomizers and Low Severity						
Late Randomizers and High Severity						
Inducted onto Study Medication						
Baseline Preference ²						
Preferred Neither Treatment						
BUP-NX Preference						
XR-NTX Preference						
Preferred Either Treatment						
Baseline Motivation ³						
Motivated for Neither Treatment						
BUP-NX Motivated						
XR-NTX Motivated						
Motivated for Both Treatments						

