	N	Mean (STD)	Median (Min, Max)	N	Mean (STD)	Median (Min, Max)
Randomization Timing Status						
Early Randomizers						
Late Randomizers						
Opioid Severity Level						
Low Severity						
High Severity						
Randomization Timing Status by Opioid Severity Level						
Early Randomizers and Low Severity						
Early Randomizers and High Severity						
Late Randomizers and Low Severity						
Late Randomizers and High Severity						
Inducted onto Study Medication						

¹ Percent days of illicit opioid use is calculated based on TLFB (only illicit use is provided) starting on Day 21 up until the day of relapse and is calculated as the number of opioid use divided by the total number of days in that time frame. Note, if the subject relapses immediately on Day 21, the percent days of opioid use is 100%. Missing TLFB days are defined as opioid use days.

Table 20: Summary of Abstinent Days¹ for Groups of Interest						
	BUP-NX (N=)			XR-NTX (N=)		
	N	Mean (STD)	Median (Min, Max)	N	Mean (STD)	Median (Min, Max)
Randomization Timing Status						
Early Randomizers						
Late Randomizers						
Opioid Severity Level						
Low Severity						
High Severity						
Randomization Timing Status by Opioid Severity Level						
Early Randomizers and Low Severity						
Early Randomizers and High Severity						
Late Randomizers and Low Severity						
Late Randomizers and High Severity						
Inducted onto Study Medication						

¹ Abstinent days are calculated based on TLFB starting on Day 21 up until the day of relapse and will be calculated as the number of days where opioids were not used. Missing TLFB days are defined as non-abstinent days.

Table 21: Summary of Number of Visits ‘Present and Clean’¹ for Groups of Interest						
	BUP-NX (N=)			XR-NTX (N=)		
	N	Mean (STD)	Median (Min, Max)	N	Mean (STD)	Median (Min, Max)
Randomization Timing Status						
Early Randomizers						
Late Randomizers						
Opioid Severity Level						
Low Severity						
High Severity						
Randomization Timing Status by Opioid Severity Level						
Early Randomizers and Low Severity						
Early Randomizers and High Severity						
Late Randomizers and Low Severity						
Late Randomizers and High Severity						
Inducted onto Study Medication						

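### SAP Tables 15-17 summarise time to relapse in relapsers only, Table 19 mixes pre-relapse use with the share relapsing at Day 21, and the event-dating table can place a relapse before Day 21

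*SAP*

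**What the plan says.** **Time to relapse.** Footnotes to Appendix A Tables 15, 16 and 17 say: "Time to relapse summary statistics are only summarized for subjects who met the relapse criteria". Table 15 shows mean, SD, median and range by arm, below the relapse counts. Table 16 shows the mean, SD, median and range by arm within timing, severity, preference, motivation and induction groups. Table 17 does so by site.

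**Percent days of use (Table 19).** The footnote counts self-reported use "starting on Day 21 up until the day of relapse and is calculated as the number of opioid use divided by the total number" (the total being the days in that span). It adds that "if the subject relapses immediately on Day 21, the percent days of opioid use is 100" per cent, and that "Missing TLFB days are defined as opioid use days". It does not say whether the relapse day itself is counted, or which day ends the window for someone who never relapses. SAP 5.3.2 sets the relapse day at the start of the qualifying period, not at its end.

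**Dating the event.** Table 4 of SAP 5.3.2 dates a four-week event whose first use week rests on a missing urine alone to the first day of that week's calendar window. A first week resting on a positive urine takes the day of that urine. The calendar in SAP 5.3.1 gives visit 3 a window of Days 17-23. SAP 5.3.1 also makes a missed visit a use week, but starts relapse assessment at Day 21. Protocol 11.1.7 says relapse cannot, by definition, precede Day 21.

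**The concern.** A mean time to relapse among relapsers compares groups selected by the outcome. If one treatment prevents relapses, those relapses leave its column altogether, and the mean of the rest need not move in step with the benefit. A reader who takes the arm columns of Tables 15-16 as the treatment contrast in time would see a fraction of it.

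Table 19 looks like a measure of how much people used before relapse. A participant who relapses at Day 21 has no earlier days in the window, so the 100% carries no information about pre-relapse use; it records the relapse. The arm mean is then a blend of two quantities. This matters here because SAP 3.2 expects failed induction to lead to relapse, and SAP 5.3.3 reports that initiation differed between arms in early randomisers. The share relapsing at Day 21 may therefore differ by arm, most of all in the early-randomiser row.

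The dating rule feeds the primary time variable. As written, two programmers could code it differently.

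**Working it through.** **Inputs from the SAP (3.3 and its Table 2).** Exponential failure, 40% six-month success, HR .633, 200 per arm, two-sided 5% logrank test.

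**The plan's own figure reproduces.** Alternative success = 0.4^.633 = .560. Events = 200 × .60 + 200 × .44 = 208. Freedman power = Φ(√208 × .367/1.633 − 1.96) = Φ(1.28) = 90.0%, as stated.

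**1. Relapser-only times.** I date relapse in whole days, put every failure up to Day 21 on Day 21, and treat Day 168 as no relapse.

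| | 40% arm | 56% arm | Gap |
|---|---|---|---|
| Mean, relapsers only | 72.9 | 77.2 | 4 |
| Median, relapsers only | 65 | 71 | 6 |
| Restricted mean, all randomised | 110.9 | 128.0 | 17 |
| Kaplan-Meier 25th percentile | 52 | 83 | 31 |
| Kaplan-Meier median | 127 | not reached | – |

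The restricted means follow from the first row: .60 × 72.87 + .40 × 168 = 110.9, and .440 × 77.19 + .560 × 168 = 128.0.

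**2. Table 19.** Let q be the share relapsing at Day 21 and m the share of pre-relapse days scored as use, including missing days. The documents give no value of m, so every m below is an assumption.

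- Relapse day excluded: arm mean = q + (1 − q)m.
- Relapse day included: a relapser with n earlier days scores (nm + 1)/(n + 1); a non-relapser scores m.
- Planning effect: q = 1 − .4^(22/168) = 11.3%, and 7.3% at HR .633.

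| Assumed use, 40% arm vs 56% arm | Excluded | Included |
|---|---|---|
| 5% vs 5% | 15.7 vs 11.9 (gap 3.8) | 17.6 vs 13.2 (gap 4.3) |
| 10% vs 5% | 20.2 vs 11.9 (gap 8.2) | 21.9 vs 13.2 (gap 8.7) |
| 5% vs 10% | 15.7 vs 16.6 (gap −0.8) | 17.6 vs 17.8 (gap −0.2) |

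In the first row pre-relapse use is identical, so the whole gap comes from relapse.

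An illustration for the early row takes the induction rates behind the SAP 3.2 decision rule, .85 on BUP-NX and .60 on XR-NTX. It assumes that everyone not inducted relapses at Day 21, that the hazard is otherwise equal (40% success), and that pre-relapse use is 10% on BUP-NX and 5% on XR-NTX. Then:

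- BUP-NX: q = .15 + .85 × .113 = .246; mean = .246 + .754 × .10 = 32.1%.
- XR-NTX: q = .40 + .60 × .113 = .468; mean = .468 + .532 × .05 = 49.4%.
- With the relapse day included: 33.6% vs 50.5%.
- If only half of those not inducted relapse at Day 21 (relapse day excluded): 26.2% vs 32.6%.

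The arm with half the pre-relapse use shows the higher figure in each case.

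**3. Dating.** Suppose visits 3 to 6 are all missed. Each is a use week, the run begins with visit 3, and Table 4 dates the event to Day 17, four days before the stated start. SAP 5.3.1 closes only the self-report route for a visit 3 attended on Day 21; it does not bar a missing urine at visit 3 from opening a run. A Day-17 event also leaves Table 19's window empty, and the Day-21 note does not cover it.

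The Cox model uses only the order of events. Moving every Day-21 event to Day 17 keeps that order, so the hazard ratio does not change. In a simulation of the planning effect with 285 per arm, moving a random half of them changed it by less than 0.005, and moving those in one arm only by less than 0.014.

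**The case against.** **The relapser-only restriction is disclosed and largely covered.** This is mostly right. The footnotes are explicit and relapse counts are printed. Kaplan-Meier Figures 6-9 show all randomised by arm, timing and severity, and Table 18 gives relapse by group. A reader might infer that the SAP offers no all-randomised view of time to relapse; it does. What stands is that the only tabulated time statistics are the conditional ones. Table 16's preference, motivation and induction rows also have no matching curve.

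**Table 19's 100% may be plain arithmetic.** If the relapse day is counted, a self-reported Day-21 relapse is one use day in one, and a missing day also counts as use. It is tempting to say that a Day-21 relapse scores 100% while a Day-22 relapse after a clean day scores 0%. That holds only if the relapse day is excluded; included, the second figure is 50%, and the footnote does not settle which applies. The blending of relapse and use survives either reading.

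**The induction figures are assumed.** Correct. The .60 is an alternative that the decision rule was built to detect, not a reported rate. Induction stays open to week 22, so not everyone uninducted need relapse at Day 21.

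**Other analyses answer this.** Table 19 has an "Inducted onto Study Medication" row, and SAP 3.6 says: "The as-treated population will consist of only participants who were inducted onto study medication". Both can remove never-inducted Day-21 relapses. Both also select on an event after randomisation, so neither is a randomised comparison.

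**It may be the modelled outcome.** A reader might infer that a secondary efficacy test rests on the Table 19 ratio, since SAP 5.5 says "continuous variables or count variables (e.g., bags per day of heroin use) will use mixed effect models depending on the distribution of the outcome" and Protocol 5.2 lists "self-report days using opioids), proportion of opioid-positive urine tests". No text says that this ratio is what will be modelled.

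**Conclusion.** Minor, and confined to description and one rule. The primary Cox analysis, the week-24 success rates and the Kaplan-Meier figures keep all randomised participants and do not share the first two faults. Nor do Tables 18, 20 and 21.

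- Tables 15-17 condition on relapse. Under the SAP's own planning effect, a 17-day difference in restricted mean appears as 4 days in the arm means. This rests on the exponential planning model.
- Table 19's arm values partly reflect the share relapsing at Day 21. This holds whichever way the relapse day is counted. It does not follow that the table will disfavour XR-NTX, or that it will mislead by any given amount: that depends on use and relapse rates that the documents do not give.
- Table 4 of SAP 5.3.2 contradicts the endpoint definition when read literally. A reader might infer that the SAP means to count relapses before Day 21. The repeated Day-21 start, and Table 19's own reference to an immediate relapse on Day 21, suggest instead that a floor was intended and left out. The effect on the hazard ratio is negligible.

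**What to change.** 1. In Tables 15-16, add the Kaplan-Meier 25th percentile and median and the restricted mean relapse-free time in all randomised, or substitute them for the relapser-only rows. The 25th percentile is needed because the median may not be reached.
2. Label Table 19 as pre-relapse use. State whether the relapse day is counted and which day ends the window for non-relapsers. Report Day-21 relapses as a separate count instead of scoring them 100%. Note that the induction row is not a randomised comparison.
3. In Table 4 of SAP 5.3.2, set any event date earlier than Day 21 to Day 21. This covers the missing-urine row, and the positive-urine row if a visit-3 urine taken on Days 17-20 can open a run.

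The cost is a few footnotes, a few output rows and one line in the dating table, all from data already collected. A fixed Day 21-167 version of Table 19 could be added as a sensitivity analysis. It would need a stated range for days after relapse, because weekly visits stop then.

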9.2 Secondary Outcomes

Table 2: Protocol Secondary Outcomes and Hypotheses

Outcomes	Hypotheses
Proportion successfully inducted onto assigned study medication (binary: did or did not receive first dose of XR-NTX, or achieve maintenance dose of BUP-NX)	BUP-NX will produce higher rate of successful induction than XR-NTX Significance/Rationale: XR-NTX induction requires completion of detoxification, whereas BUP-NX induction only requires onset of withdrawal symptoms. Thus XR-NTX may have more dropouts after randomization but prior to XR-NTX induction.
Adverse Events related to study medications	XR-NTX and BUP-NX will produce equivalent rates of SAEs, and equivalent rates of AEs, though AE pattern will differ somewhat (e.g. injection site reactions with XR-NTX) Significance/Rationale: Careful documentation of SAEs and AEs, including overdose episodes, would be considered essential safety data, and important component of a comparative effectiveness trial.
Opioid abstinence over time while on study medication (Weekly TLFB, confirmed by urine drug screens)	XR-NTX will produce greater opioid abstinence than BUP-NX Significance/Rationale: XR-NTX produces complete blockade of opioid effects, so that during treatment with monthly injections, opioid use can be expected to be minimal. In contrast BUP-NX may not produce complete blockade, or patients may reduce or stop doses for a few days and substitute other opioids (heroin, prescription opioids).

Outcomes	Hypotheses
Alcohol and other drug use, over time (TLFB and UDS)	
XR-NTX will be superior to BUP-NX in producing abstinence from alcohol and other drugs
 
Significance/Rationale: Clinical trials show XR-NTX is effective for treatment of alcohol dependence, and naltrexone has some evidence of efficacy for stimulant dependence.

Cigarette smoking (FTND, Tobacco Use Questionnaire, VAS nicotine craving)	
XR-NTX will reduce cigarette smoking compared to BUP-NX
 
Significance/Rationale: Naltrexone has been studied as a treatment for nicotine dependence, with some support from clinical trials, although inconsistent. Given high morbidity and mortality associated with nicotine dependence, a comparative advantage of one or the other of these treatments at reducing smoking would be valuable to examine.

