5.3 Primary Outcome

The primary outcome measure will be the time to the event, with the event called relapse. By definition individuals are abstinent at the time of randomization. Relapse occurs if the participant is using any non-protocol prescribed opioids regularly starting at day 21 post-randomization or thereafter. Operationally, loss of persistent abstinence is defined as either: (a) four consecutive opioid use weeks, or (b) seven consecutive days of use by self-report. A use week is defined as any week during which a participant self-reports at least one day of use during that week, provides a urine sample positive for non-protocol opioids, or fails to provide a urine sample.

Self-report of opioid (heroin or prescription opioids) and other substance use will be ascertained at each weekly study visit using the Time Line Follow-back for each day leading back to the previous visit. Urine will be collected at each study visit and tested for opioids. In the event that a participant reports no use, but their urine test indicates use, then we will regard the week as a use week. Missing urine samples will be classified as positive. The time of the event occurs at the start of the qualifying clinical event period (e.g., first of the 7 consecutive use days or start of the 4 consecutive weeks of use).

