5.5.2 Opioid Abstinence

Opioid abstinence will be measured using the TLFB and confirmed by urine drug screens.

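### Opioid abstinence is defined as self-report confirmed by urine, but SAP Tables 19 and 20 count days from self-report alone and no listed table shell gives a urine-confirmed measure

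*SAP*

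**What the plan says.** **The outcome.** SAP 5.5.2 is a single sentence: "Opioid abstinence will be measured using the TLFB and confirmed by urine drug screens". Protocol 9.2 (Table 2) and SAP 2.2 (Table 1) describe the outcome in the same terms and attach a directional hypothesis, that XR-NTX gives greater abstinence than BUP-NX. No section states how a urine result confirms or overrides the reported days.

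**A second wording.** Protocol 5.2, objective 1c, lists two measures together: "Opioid abstinence, as measured by the Timeline Follow-Back (TLFB) (self-report days using opioids), proportion of opioid-positive urine tests".

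**The derivations.** The SAP Appendix A footnotes contain the only written day-level rules.
- Table 19: "Percent days of illicit opioid use is calculated based on TLFB (only illicit use is provided) starting on Day 21", up to relapse.
- Table 20: "Abstinent days are calculated based on TLFB starting on Day 21 up until the day of relapse". Its only adjustment is "Missing TLFB days are defined as non-abstinent days". Table 19 likewise counts missing TLFB days as use.
- Table 21: a count of visits with a valid, negative urine from Day 21 to relapse, with no reference to TLFB.

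**The primary endpoint.** SAP 5.3 handles a conflict between the two sources explicitly: "In the event that a participant reports no use, but their urine test indicates use, then we will regard the week as a use week".

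**The concern.** The definition calls for confirmation, and the day-level rules apply none. A participant who attends, denies use and tests positive is credited with a full week of abstinence, while one whose TLFB is missing is charged with use. Evidence against the denial is therefore treated more leniently than no evidence. The primary endpoint takes the opposite line and lets the urine override the denial.

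The trial is open-label to staff and participants (Protocol 8.7), so willingness to admit use could differ by arm. On a self-report-only count, such a difference would pass directly into the comparison on an outcome with a stated superiority hypothesis. Weekly urines are collected and could serve as the check.

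**Working it through.** The plan states no figure to reproduce. The check applies the footnotes and the relapse rule to hypothetical records.

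**Inputs**
- Relapse: four consecutive use weeks, or seven consecutive self-reported use days (SAP 5.3).
- Where the first use week rests on urine alone, relapse starts on the day of that positive urine (SAP 5.3.2, Table 4).
- Visit targets: week 4 is Day 27 and week 24 is Day 167, which gives 21 weekly urines (SAP Table 3).
- TLFB runs from the previous attended visit to the day before the current one (SAP 5.3.1).

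**Assumptions.** All use is denied, TLFB is complete, every urine is given on its target day, and positive urines are true positives.

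**Window.** Day 21 to Day 167 inclusive is 167 − 21 + 1 = 147 days. Stopping the day before the Day 167 visit gives 146. The week 4 interval contributes 6 days and the other 20 weeks contribute 7 each: 6 + 20 × 7 = 146.

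**Most positives without relapse.** Each block of four weeks needs at least one negative. The 21 weeks hold five full blocks plus one week, so at least 5 are negative and at most 21 − 5 = 16 are positive.

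**Results on the 146-day window.** The confirmed column counts only days leading to a negative urine.

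| Urine pattern, weeks 4–24 | Positive | Relapse | Table 20 days | Table 19 use | Confirmed days |
|---|---|---|---|---|---|
| Three weeks in four | 16 of 21 | none | 146 | 0% | 5 × 7 = 35 |
| Alternate weeks | 11 of 21 | none | 146 | 0% | 10 × 7 = 70 |
| One week in four | 6 of 21 | none | 146 | 0% | 15 × 7 = 105 |
| All from week 12 | 13 of 21 | Day 83 | 62 | 0% | 62 − 7 = 55 |
| All from week 4 | 21 of 21 | Day 27 | 6 | 0% | 0 |

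**Overstatement per discordant week.** A positive urine shows some use, which may be one day or all seven. The overstatement is therefore 1 to 7 days times the number of discordant weeks. For the 16-week record this is 16 × 1 = 16 to 16 × 7 = 112 days. On the 146-day window the upper end is 146 − 35 = 111, because the first interval has only six countable days.

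**Assumed discordance rates over 21 weeks** (the documents give none)

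| Rate | Discordant weeks | Overstatement |
|---|---|---|
| 5% | 1.05 | about 1 to 7 days |
| 10% | 2.10 | about 2 to 15 days |
| 15% | 3.15 | about 3 to 22 days |
| 20% | 4.20 | about 4 to 29 days |

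**The case against.** **Two wordings exist.** Objective 1c sets self-reported use days beside the proportion of positive urines, and Tables 19 to 21 broadly follow that layout. This stands: a TLFB-only row is legitimate and its basis is disclosed. It does not supply the confirmed measure that SAP 5.5.2 and both outcome tables name, and Table 21 is a count of clean urines, not the proportion in objective 1c.

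**The shells are not exhaustive.** A reader might infer that the confirmed outcome will never be computed. The documents do not support that. Appendix A also has no shell for the primary Cox hazard ratio or the induction logistic model, although both are planned, and SAP 5.5 promises models for secondary outcomes. Nor is Table 19 or 20 labelled as the 5.5.2 outcome, which concerns abstinence while on study medication. What can be shown is that the confirmation rule is unwritten and that no listed shell applies one.

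**Urine is not wholly absent.** It helps set the relapse date that closes the window, so a continuously positive participant gains few days. The 16-of-21 record is a constructed extreme.

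**Urine has its own asymmetries.** Buprenorphine counts as use only in the XR-NTX arm (SAP 5.3.1). The naltrexone label in Protocol Appendix C (5.11) also warns of cross-reactivity with certain opioid immunoassays. Charging seven use days for each positive urine could therefore replace under-counting with over-counting, unequally by arm. This stands and shapes the fix.

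**Conclusion.** The concern holds in a limited form. The plan defines abstinence as confirmed self-report, but its only day-level derivations are unconfirmed, and followed literally they can credit full abstinence to a participant with up to 16 of 21 positive urines. The size is 1 to 7 days per discordant week: 16 to 112 days for that extreme record, and about 1–7 to 4–29 days at assumed discordance of 5% to 20% in a participant followed to Day 167.

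Two stronger readings are tempting. One is that every discordant week adds seven false days. Seven is only the upper bound, since one positive urine does not establish daily use. The other is that the tables favour a particular arm. Without discordance rates by arm, neither the direction nor the size of any such bias can be computed. The primary endpoint is not affected. The change is worth making because it carries out the plan's own definition with data already used together for the primary endpoint.

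**What to change.** - **SAP 5.5.2 and Table 20:** add a urine-confirmed row and name it as the 5.5.2 abstinence outcome. TLFB days in a visit interval (as set out in SAP 5.3.1) count as abstinent only if no use is reported on the day and that week's urine is provided, valid and negative for non-protocol opioids on the arm-specific panel in 5.3.1. Days with a missing, adulterated or out-of-temperature urine are not confirmed abstinent.
- **Tables 19 and 20:** keep the TLFB figures and label them *self-report only*.
- **Table 19:** do not convert whole intervals into use days on the strength of one urine.

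**Cost.** Footnote wording, one extra row and modest programming; no new data are needed. The downside is that one positive or missing urine leaves a whole interval unconfirmed, and any assay cross-reactivity carries over from the primary rule. The retained self-report row shows how much difference the confirmation rule makes.
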